9.2.2 Neutralizing anti-bimekizumab antibodies

NAb will be assessed using IL-17AA- and IL-17FF-specific assay method, respectively. NAb results will be positive or negative to each specific NAb assay or both.

All NAb results derived from samples with drug concentrations > the drug tolerance limits of the NAb assays (100µg/mL) will be labeled 'inconclusive'. All inconclusive results will be regarded as missing.

Subjects will be assigned an overall Neutralizing anti-BKZ antibodies (NAb) classification, inclusive of Baseline and post-Baseline results from NAb assay:

- NAb negative: No NAb positive samples for IL-17AA and IL-17FF at Baseline or post-Baseline. This group will also include subjects who have only 1 missing sample and all other available samples during the period of interest are negative. Subjects who are NAb negative will be classified as follows:
 - ADA_b positive / NAb negative: ADA_b positive subjects who are 1) NAb negative for all available ADA_b positive samples or 2) with only 1 missing NAb sample and all other evaluated ADA_b positive samples are NAb negative.
 - ADA_b negative: if the subject has all the samples as ADA_b negative or only 1 missing/inconclusive sample with all other available samples as negative ADA_b. Note that ADA_b negative samples are not subject to the neutralizing assay.
- NAb positive: One or more positive samples (IL-17AA positive, IL-17FF positive, or both) at Baseline or post-Baseline (regardless of missing samples). Subjects who are NAb positive will be further classified as follows:
 - Positive for IL-17AA only: 1 or more positive samples for IL-17AA at Baseline or post-Baseline. No positive samples for IL-17FF
 - Positive for IL-17FF only: 1 or more positive samples for IL-17 FF at Baseline or post-Baseline. No positive samples for IL-17AA
 - Positive for both IL-17AA and IL-17FF: 1 or more positive samples for both IL-17AA and IL-17FF at Baseline or post-Baseline

- NAb Missing: more than one relevant NAb samples are missing/inconclusive and other available NAb samples during the period of interest are negative, missing or insufficient sample left for NAb testing.

Note: For PK and efficacy analyses up to a certain timepoint (Week 16) by NAb status, only data up to the timepoint of interest will be utilized in deriving the subject's overall NAb status during that period (eg for the ACR50 by NAb up to Week 16, only NAb data from Baseline up to Week 16 will be used to derive subject's overall NAb status during the 16-week Double-Blind Treatment Period).

A listing will be produced to summarize the NAb status overall in the study. The listing will be sorted by treatment group, subject identifier and visit and will summarize the following information for each subject assessed for NAb:

- Visit
- Study week
- Laboratory sampling date and time
- Time since previous dose (weeks)
- The corresponding BKZ plasma concentration level at each visit (ug/mL)
- Anti-BKZ anti-body titer at each visit
- IL-17AA NAb status and corresponding IL-17AA signal/negative control result
- IL-17FF NAb status and corresponding IL-17FF signal/negative control result

A summary table will provide the following overall summary statistics by treatment group (based on the total number of subjects in the SS):

- The number and percentage of subjects confirmed as anti-BKZ antibody positive and anti-BKZ antibody negative to Week 16 (excluding SFU), 16 (including SFU).
- The number and percentage of subjects who are NAb positive, NAb negative and missing to Week 16 (excluding SFU), 16 (including SFU).

The NAb summary tables will be repeated with percentages calculated on a denominator based on the number of ADAb positive subjects during the above periods.

In addition, the following analyses will be performed to assess the impact of NAb status on efficacy variables:

- A figure summarizing efficacy response (ACR50 based on NRI) versus time for each treatment group by NAb status (ADAb negative, NAb positive, ADAb positive/ NAb negative, missing) will be created. If $\geq 95\%$ of subjects are included in the non-missing groups, the missing group will not be displayed in the figure. Separate figures will be presented for data up to Week 16. The data will also be presented in a tabular format. The analyses will be repeated for ACR20 and PASI90. The data will be also presented in a tabular format.

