In addition, the table summaries and figures will be repeated by neutralizing anti-bimekizumab antibodies (NAb) status (ADA b negative, NAb positive, ADA b positive / NAb negative, missing, [Section 9.2.2](#)). Tables and figures will be generated for concentration data up to weeks 16. For these tables and figures: the NAb status will be determined on a subject-level basis (ie not on a visit level) according to the categories in [Section 9.2.2](#). For BKZ160mg Q4W dose group: the NAb status will be determined based on data from the Baseline visit (pre-dose sample on study day 1) up to Week 16 NAb sample (eg if a subject has no positive NAb samples for IL17AA or IL17F from Baseline up to Week 16, that subject will be assigned a NAb negative status for all visits of the initial treatment period).

The NAb status will be re-derived and updated with SFU data for the final study analysis, followed by an update to the relevant tables and figures.

PK samples collected at scheduled visits (except the SFU visit) and meeting the following requirements will be included in summaries and corresponding figures. Samples not meeting the following requirements will be excluded:

- For PK samples associated with the ET visit: include samples collected >14 days and <42 days after the last/previous dose received
- For PK samples associated with all other visits (Week 4, 8, 12, 16): include samples collected >14 days after the preceding dose, <42 days after the preceding dose, and no later than 1 hour after the current visit dose including unscheduled assessments as described in [Section 3.1](#).
- For the SFU visit, all concentrations obtained at the SFU visit will be included in the summary tables but will not be included in the figures.

When multiple samples meeting the criteria above are associated with the same visit (either because multiple samples were collected or due to remapping or unscheduled visits), only results from one valid sample will be included in summaries and figures using the following rules. All others will be excluded and only listed:

- For PK samples with different dates, the sample that is closest to the target visit date will be included. For samples with different dates that are the same distance to the target visit date, the sample collected prior to IMP dosing will be included.
- For PK samples with the same date, the first sample as provided in the raw data will be included.

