- Summary tables displaying the number and percentage of subjects with ADAb status (positive, negative, or missing) at the time of each visit by treatment group (160mg Q4W) will be provided. For the placebo arm, the by-visit summary of ADAb positive status will include a summary of subjects with ADAb status (positive, negative, or missing) at Baseline and Week 16. For the overall summary at any visit (only applicable to 160mg Q4W dose arm), two summaries will be presented: one that will exclude data obtained at the SFU visit and will include data obtained at Baseline and one that will include data obtained at both the SFU visit and at Baseline. Subjects who rolled over to the OLE study will not have a SFU visit per study protocol. For these subjects, the ‘overall ADAb status including SFU’ will then be considered as being identical to the ‘overall ADAb status up to Week 16’.

For the overall ADAb status, a subject will be classified as:

- Positive if the subject has at least one positive sample at any time in the treatment period (regardless of having missing /inconclusive data)
- Negative if the subject has all the samples negative or only one missing/inconclusive sample with negative ADAb samples up to the timepoint of interest
- Missing if the subject has missed more than one sample result for ADAb assessment (or have more than one inconclusive sample) and all other available ADAb samples are negative during the period of interest (If there are $\geq 95\%$ of subjects included in the non-missing groups, the missing group will not be displayed on the table).

The above summary table displaying the number and percentage of subjects in each of the ADA_b status (positive, negative, total of positive and negative, missing) will be repeated for the subgroup of Japan.

- A summary table displaying the number and percentage of subjects in each of the ADA_b status (positive, negative, total of positive and negative, missing) by concomitant medications (use of cDMARDs at entry, use of methotrexate at entry, use of oral/systemic corticosteroids at entry) will be provided (overall summaries only).
- A table displaying the number and percentage of subjects with the first occurrence of any ADA_b positivity during the study (ie, including Baseline visit) will be summarized. This summary will include the following categories:
 - Any ADA_b+: ADA positive sample regardless of category during the treatment period

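### Section 9.2.2 labels a subject NAb negative with no NAb result at all when the only ADAb-positive sample has a missing or inconclusive NAb test

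*SAP*

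**What the plan says.** The classification follows from these statements in the SAP:

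- **Overall ADAb status (Section 9.2.1).** One positive sample is enough: "Positive if the subject has at least one positive sample at any time in the treatment period".
- **Which samples are tested for NAb (Section 9.2.2).** "Note that ADA_b negative samples are not subject to the neutralizing assay".
- **Inconclusive results (Section 9.2.2).** "All inconclusive results will be regarded as missing".
- **NAb negative, parent rule (Section 9.2.2).** No NAb-positive sample, with one gap tolerated: "This group will also include subjects who have only 1 missing sample and all other available samples during the period of interest are negative".
- **ADAb positive / NAb negative, second limb (Section 9.2.2).** A subject "with only 1 missing NAb sample and all other evaluated ADA_b positive samples are NAb negative".
- **NAb Missing (Section 9.2.2).** "NAb Missing: more than one relevant NAb samples are missing/inconclusive and other available NAb samples during the period of interest are negative". The sentence closes with a reference to samples that were missing or too small to test.
- **Worked example for PK (Section 9.1).** Where no NAb-positive sample is seen from Baseline to Week 16, "that subject will be assigned a NAb negative status for all visits of the initial treatment period".

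The resulting groups are used for the NAb summary tables and the ACR50, ACR20 and PASI90 displays (Section 9.2.2), the PK tables and figures (Section 9.1) and the TEAE table by NAb status (Section 10.2.1). The TEAE table lists three groups and has none for missing NAb status.

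**The concern.** A tolerance of one missing result is reasonable when several results exist and the rest are negative. For NAb the number of relevant samples is the number of ADAb-positive samples, and that can be one. The tolerance then covers the subject's entire NAb information, and the subject is reported as negative on no measurement.

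At stake is the meaning of the ADAb positive / NAb negative group. It serves as the comparator that shows whether neutralizing activity, rather than binding antibody alone, goes with lower concentrations, lost response or more adverse events. Untested subjects blur that comparison, and the tables understate how incomplete the NAb testing was. The TEAE table has no missing group, so these subjects appear there as NAb negative with nothing to mark them.

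**Working it through.** **Step 1: apply the rules to every pattern.** Let k be the number of ADAb-positive samples and m the number of these with a missing or inconclusive NAb result, with no NAb-positive result. Sampling is at all visits except Screening (Section 2.2.3.5), which gives five samples to Week 16: Baseline and Weeks 4, 8, 12 and 16. So k runs from 1 to 5 and m from 0 to k, which gives 2 + 3 + 4 + 5 + 6 = 20 patterns.

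| k | m | Valid NAb results | Group under Section 9.2.2 |
|---|---|---|---|
| 1 | 0 | 1 | ADAb positive / NAb negative |
| **1** | **1** | **0** | **ADAb positive / NAb negative** |
| 2 | 0 or 1 | 2 or 1 | ADAb positive / NAb negative |
| 2 | 2 | 0 | NAb Missing |
| 3 to 5 | 0 or 1 | at least 2 | ADAb positive / NAb negative |
| 3 to 5 | 2 or more | k − m | NAb Missing |

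Exactly one pattern puts a subject with no valid result in the negative group: k = 1, m = 1. The parent rule admits it (no positive, one missing). The second limb is met because there is no other sample to contradict it. NAb Missing is not met because m is not above 1. All other patterns with nothing tested (k = m = 2 to 5) go to NAb Missing.

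**Step 2: effect on the reported percentages.** The SAP states no ADAb, NAb or missing-result rate, so there is no figure to reproduce. For illustration, take the planned 260 bimekizumab subjects (Section 2.4) and these assumptions, none of which is from the SAP:

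- a = share ADAb positive, 20% to 40%
- s = share of those with a single positive sample, 20% to 40%
- u = share of those single samples without a valid NAb result, 2% to 10%
- q = true NAb-positive share among ADAb positives, 20% to 40%
- all other ADAb-positive subjects are taken as evaluable

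Formulas: ADAb positive A = 260a; untested x = A·s·u; NAb positive = q(A − x); NAb negative as written = (1 − q)(A − x) + x; NAb negative with a valid result required = (1 − q)(A − x).

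| | Low corner (a 0.2, s 0.2, u 0.02, q 0.2) | High corner (a 0.4, s 0.4, u 0.10, q 0.4) |
|---|---|---|
| A | 52 | 104 |
| x | 52 × 0.2 × 0.02 = 0.21 | 104 × 0.4 × 0.10 = 4.16 |
| NAb negative / A, as written | 41.64 / 52 = 80.1% | 64.06 / 104 = 61.6% |
| NAb negative / A, valid result required | 41.43 / 52 = 79.7% | 59.90 / 104 = 57.6% |
| Untested share of NAb-negative group | 0.21 / 41.64 = 0.5% | 4.16 / 64.06 = 6.5% |
| NAb positive / A, under either rule | 10.36 / 52 = 19.9% | 39.94 / 104 = 38.4% |
| NAb positive / 260, under either rule | 4.0% | 15.4% |

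The NAb-negative share of ADAb positives falls by s·u, that is 0.4 to 4.0 points, and the missing share rises by the same amount. The NAb-positive share does not move. Section 9.2.2 uses all Safety Set subjects and all ADAb-positive subjects as denominators, and both keep missing subjects in.

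**The case against.** **The natural reading.** The second limb speaks of other evaluated samples, which suggests that at least one exists, and the NAb Missing rule ends by mentioning samples that could not be tested. A programmer might therefore code the single-sample case as Missing. This stands as a possible reading. But the ending sits under a threshold of more than one sample, the parent rule admits the subject without any such presumption, and the Section 9.1 example points to negative. On the kindest view the case is ambiguous, which still needs a wording change.

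**A deliberate convention.** The SAP treats one missing result as negative elsewhere. Overall ADAb status in Section 9.2.1 tolerates one, and Section 9.1 explicitly classes a missing or inconclusive Baseline sample as negative for cumulative ADAb status. That is fair for ADAb. Section 9.2.2 makes no such explicit statement for a lone NAb sample, and it sends a subject with two untested samples to Missing, so the convention is not applied consistently to equally untested subjects.

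**A rule that might absorb the case.** One efficacy figure in Section 9.2.1 counts a subject with a single positive sample as ADAb negative. That definition belongs to that figure and its table and does not govern Section 9.2.2.

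**Limited consequence.** The displays are descriptive, the numbers are probably small, and the comparator is distorted only to the extent that untested subjects differ from true NAb negatives. All of this stands.

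**A stronger reading.** A reader might infer that the rule understates NAb incidence. The document does not support that. Moving the untested subjects to Missing leaves the NAb-positive percentage unchanged on both planned denominators. Any shortfall against the truth comes from the missing assay results, and only if some of those subjects are truly NAb positive. The percentage would rise only on a denominator of NAb-evaluable subjects, which the SAP does not use.

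**Conclusion.** The point holds as a classification defect. As written, Section 9.2.2 assigns ADAb positive / NAb negative to a subject with one ADAb-positive sample and no valid NAb result, while equally untested subjects with more positive samples are classed as Missing. The direct effects are an overstated NAb-negative share, an understated NAb-missing share, and untested subjects in the NAb-negative comparator for the PK, efficacy and TEAE displays.

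The size cannot be determined from the SAP. Under the assumed ranges it is 0.2 to 4.2 subjects of 260, or 0.5% to 6.5% of the ADAb positive / NAb negative group. Nothing in the testing hierarchy of Section 4.5 depends on it. It merits correction because the rule gives a wrong label and the change is cheap, not because a main conclusion is at risk.

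**What to change.** 1. In Section 9.2.2, define ADAb positive / NAb negative by three conditions: at least one ADAb-positive sample has a valid NAb result, every valid result is negative, and no more than one result is missing or inconclusive. Make the parent NAb-negative rule consistent with this for ADAb-positive subjects.
2. In the same section, assign any ADAb-positive subject without a valid NAb result to NAb Missing, however many samples are missing.
3. In Section 9.1, align the example so that absence of a NAb-positive sample does not by itself give NAb-negative status to an ADAb-positive subject.
4. In Section 10.2.1, add a NAb Missing column to the TEAE table by NAb status, so that the moved subjects have a place.

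The cost is one derivation condition, a few lines of text and one table column. A few subjects move to Missing. In the efficacy figure by NAb status the missing group is not displayed when at least 95% of subjects are in the other groups, so a footnote with the number omitted would keep them visible.

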10 SAFETY ANALYSES

All safety summaries will be done on all subjects in the SS.

10.1.1 Extent of exposure and time at risk

The extent of exposure will be evaluated based on the duration of exposure to IMP and the time at risk. Two summary tables will be created to describe the extent of exposure.

The first table consists of a descriptive summary of study medication duration (in days), total study medication duration (in subject-years), and total time at risk (in subject-years).

The sum of all durations of exposure (in subject-years) will be calculated as:

$$\frac{\sum_{Subjects} \text{Duration of exposure (days)}}{365.25}$$

The sum of all times at risk (in subject-years) will be calculated as:

$$\frac{\sum_{Subjects} \text{Times at risk (days)}}{365.25}$$

A second summary will be created on the cumulative study medication duration for subjects exposed to the following durations of time:

- > 0 week
- ≥ 4 weeks
- ≥ 8 weeks
- ≥ 12 weeks
- ≥ 16 weeks

The study medication duration (in days) will be calculated as follows:

$$\text{Date of last dose} - \text{Date of first dose} + 28$$

- If the date of last dose + 28 days extends to a date beyond the final visit date (not including SFU), then this calculation reverts to:

$$\text{Date of last visit (not including SFU)} - \text{Date of first dose} + 1$$

- For subjects who die, this calculation reverts to:

$$\text{Date of death} - \text{Date of first dose} + 1$$

The time at risk (in days) will be calculated as follows:

- For subjects who complete the study as planned and continue into the OLE study (and, therefore do not have a SFU visit):

$$\text{Date of last visit} - \text{Date of first dose} + 1$$

- For subjects who die prior to the final visit, this calculation reverts to:

$$\text{Date of death} - \text{Date of first dose} + 1$$

- For all other subjects, this calculation reverts to the minimum of the following:

Date of last dose – Date of first dose + 141

Date of last clinical contact – Date of first dose + 1

Note: 140 days refer to 5 times the half-life of BKZ.

Date of last clinical contact for each subject is defined as the maximum of [last visit date including SFU visit, last AE start date (including imputed AE start dates), date of study termination or completion, last date of study drug administration].

This group of subjects could include subjects who discontinue early from the study, subjects who complete study as planned but chose not to continue into the OLE study, or subjects who are ongoing in the SFU Period at the time of the data snapshot.

A by-subject listing of date of first and last dose and the duration of exposure will be performed.

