2.3.2 Study periods

The following study periods are defined for the classification by study period:

Screening Period (≥14 days to ≤35 days)

Starts at time of the informed consent date (Screening Visit - Visit 1) and ends the day before the first dose administration of IMP (Baseline Visit – Visit 2) (ie, generally the day before Visit 2 date). This period should last between 14 to 35 days and will involve obtaining laboratory data and verifying that the doses of nonsteroidal anti-inflammatory drugs (NSAIDs) or permitted DMARDs, if used to treat PSA, are stable. The Screening Period will also enable washout of any medications not permitted for use during the study.

Double-Blind Treatment Period (16 weeks)

Starts on the day of first dose administration of study drug (Visit 2). This period should last 16 weeks maximum. During the Double-Blind Treatment Period, subjects will be randomized 2:1 (stratified by region and prior TNF α inhibitor exposure [inadequate response to 1 or 2 prior TNF α inhibitors, or intolerance to TNF α inhibitors]) to receive 1 of 2 blinded treatment regimens:

- Bimekizumab 160mg sc Q4W,
- Placebo

Visit windows of ± 3 days are allowed from the first dose at all visits through Week 16. The visit window is relative to the Day 1 (Baseline) Visit.

Bimekizumab and placebo will be administered sc by unblinded study personnel at the clinical site.

The time between IMP doses should be ≥ 21 days and ≤ 35 days during the Double-Blind Treatment Period.

Subjects discontinuing IMP during the Double-Blind Treatment Period will return for all scheduled visits through Week 16 and the SFU Visit (20 weeks after the final dose of IMP) as applicable. Subjects withdrawing from the study will have an Early Termination (ET) Visit and a SFU Visit 20 weeks after the final dose of IMP, as applicable.

The end of the 16-week Double-Blind Treatment Period will be either the date of Week 16 visit (Visit 6) for subjects completing the treatment period, or the date of the early termination (ET) visit for subjects who discontinued during the Treatment Period.

If a subject does not have a Visit 6 or ET visit, then either the date of the last scheduled or unscheduled visit during the Treatment Period or the date of last known dose of study drug during the Treatment Period, whichever is later, will define the end date of the Treatment Period.

Safety Follow-Up

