6.4 Prior and concomitant medications

Prior medications include any medications that started prior to the start date of the first IMP administration.

Concomitant medications are medications taken at least one day in common with the study medication dosing period.

The IMP dosing period corresponding to the combined Double-Blind Treatment Period will be calculated as follows:

- The study medication dosing period start date is defined as the date of first dose.

The study medication dosing period stop date is defined as follows:

- For subjects who are ongoing at the time of the clinical data cut (not including subjects who are in SFU) use date of last clinical contact
- For subjects who died prior to last visit (not including those who died during SFU), use the minimum of the following:
 - Date of death
 - Date of last dose of any study medication + 28 days
- For subjects who complete the study as planned, the dosing period ends at the later of the following two dates:
 - Date of last administration of IMP + 28 days
 - The last scheduled visit date not including SFU
- For all other subjects, use the maximum of the following:
 - Date of last dose of any study medication + 28 days
 - Date of last visit (not including SFU)

In the case of missing data, the classification of medications as prior or concomitant will be performed as described in [Section 4.2.4](#). Imputations of missing data will be performed before calculation of relative study days.

The number and percentage of subjects taking prior medications and prior Anti-TNFs (excluding past psoriasis medications) will be summarized on the SS by treatment group, overall and by ATC class, presenting Anatomical Main Group (ATC Level 1), Therapeutical/Pharmacological Subgroup (ATC level 3), and preferred term (PT).

The table summary will be ordered alphabetically for the ATC class and in terms of decreasing frequency for PT within ATC class in the BKZ treatment group. In the event of ties, PT will be ordered alphabetically.

A by-subject listing of all prior medications and prior Anti-TNFs and concomitant medications on the SS as well as glossary of all medical medications will be provided.

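### Study medication duration runs to the date of death with no limit at last dose + 28 days, so deaths after dosing coverage ended are credited with too much exposure

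*SAP*

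**What the plan says.** Section 10.1.1 introduces the rule with "The study medication duration (in days) will be calculated as follows". It has three parts:

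- **Base rule:** last dose minus first dose, plus 28 days.
- **Cut-back:** "If the date of last dose + 28 days extends to a date beyond the final visit date", with SFU visits left out, duration becomes last visit minus first dose plus 1.
- **Death branch:** "For subjects who die, this calculation reverts to" death minus first dose plus 1. No other condition is attached.

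Two neighbouring rules treat deaths differently:

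- **Time at risk, also in Section 10.1.1:** its death branch is restricted, "For subjects who die prior to the final visit, this calculation reverts to". All remaining subjects are limited by last dose + 141 days or last clinical contact.
- **Dosing period, Section 6.4:** "For subjects who died prior to last visit (not including those who died during SFU), use the minimum of the following", where the two dates are the death itself and "Date of last dose of any study medication + 28 days". Deaths during SFU do not enter this branch.

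The durations feed a descriptive table in days and subject-years, and a cumulative table whose top row is ≥16 weeks.

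**The concern.** The base rule treats each injection as covering 28 days, and the cut-back keeps SFU time out of the count. The death branch does neither. A subject who stopped dosing and died months later is credited with all the intervening time as time on study medication. Two subjects with identical dosing then have different medication durations only because one of them died.

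At stake are the exposure tables. Total subject-years on medication is inflated in whichever arm such a death falls, and a subject dosed once can be counted among those exposed for at least 16 weeks.

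**Working it through.** **Inputs.** Count days from the first dose (day 0). L is the last dose, V the last non-SFU visit and D the death. The rules come from Section 10.1.1. Section 7 gives four injections, the last at Week 12 (nominal L = 84). Section 2.3.2 gives the SFU as 20 weeks (140 days) from the final dose and a visit window of ±3 days. Section 2.4 gives 390 planned subjects. Assumption: one week is 7 days, so the ≥16 weeks row starts at 112 days; the SAP states no conversion.

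**The plan's own figure.** For a completer on schedule, L = 84 and V = 112. L + 28 = 112 does not pass V, so duration is 112 days, exactly 16 weeks. The rule reproduces the top row.

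**Death branch.** Let a be the days from last dose to death, so D = L + a.

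- Rule as written: D + 1 = L + a + 1.
- Base rule for the same dosing: L + 28.
- Excess: (L + a + 1) − (L + 28) = a − 27, which is positive once a exceeds 27.

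| Doses | L | a | As written | Base rule | Excess |
|---|---|---|---|---|---|
| 1 | 0 | 28 | 29 | 28 | 1 |
| 1 | 0 | 60 | 61 | 28 | 33 |
| 1 | 0 | 112 | 113 (16.1 weeks) | 28 | 85 |
| 4 | 84 | 112 | 197 | 112 | 85 |
| 4 | 84 | 140 | 225 (32.1 weeks) | 112 | 113 |

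A subject dosed once enters the ≥16 weeks row if death comes 111 or more days after that dose (111 + 1 = 112).

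**Size.** The excess at a = 140 is 113 days, and 113 / 365.25 = 0.31 subject-years. If all 390 subjects had 112 days, the planned total would be 390 × 112 / 365.25 = 119.6 subject-years, so one such death adds 0.31 / 119.6 = 0.26%. This compares with the last dose + 28 limit only. If the final-visit cut-back would also have applied, the excess grows by the days cut back.

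**Completers, for the presentation note.** For survivors, base rule and cut-back together equal min(L + 28, V + 1). "Visit windows of ± 3 days are allowed from the first dose at all visits through Week 16", so L runs from 81 to 87 and V from 109 to 115, which gives 49 pairs.

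- L = 81 to 83 (Week 12 dose early): 109 to 111 days whatever V is; 21 pairs below 112.
- L = 84 to 87 (dose on time or late): 110 or 111 days if V is 109 or 110; 8 pairs below 112.
- The other 20 pairs give 112 to 115 days.

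These are counts of combinations, not a forecast share of subjects.

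**The case against.** The case for leaving the text alone has four parts.

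- **The effect is negligible.** Only deaths more than 27 days after the last dose are touched. EAIR and EAER (Section 10.2.3) use time at risk, not medication duration. No efficacy result or test depends on it. This stands and sets the weight of the point.
- **Section 6.4 has another purpose and is not an exact template.** It classifies concomitant medication. Its minimum rule leaves out SFU deaths, which fall to branches taking the later of last dose + 28 days and the last non-SFU visit. This also stands, so copying the Section 6.4 minimum to every death would not reproduce Section 6.4, and would omit the cut-back in Section 10.1.1. It does not rescue the present branch: Section 6.4 does not extend the dosing period to a late death in SFU.
- **Time at risk properly runs past dosing.** True, but its death branch carries a restriction that the medication-duration branch lacks. Sections 10.1.2.1 to 10.1.2.3 likewise switch off their death rule when death is more than 140 days after the last dose. Limits on death branches are the pattern in this plan.
- **The completer counts show no error.** A reader might infer that the tables are wrong in both directions, with a large share of in-window completers misplaced below 16 weeks. The SAP does not support that. Days of 109 to 111 are the correct duration under its own definition, and subject-years are undistorted. Receipt of injections is reported separately in Section 7. Of the 29 short pairs, 21 already fall short under the base rule because the Week 12 dose was early; the cut-back alone accounts for 8. Any percentage of subjects would rest on visit timings that the document does not give.

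**Conclusion.** The death branch of study medication duration is defective as written. It credits time after dosing coverage ended, departs from the restricted time-at-risk branch beside it, and conflicts with Section 6.4. Any death more than 27 days after the last dose is overstated by at least the days beyond 27, which can put a subject dosed once in the ≥16 weeks row.

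The practical weight is small: against the 28-day limit, at most about 0.31 subject-years per death by day 140 after the last dose, or about 0.26% of a planned total near 120. That total assumes every subject has 112 days. The number of such deaths is unknown from the document. The safety rates do not change.

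For completers there is only an optional presentation point: the ≥16 weeks row should state its day threshold.

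**What to change.** In Section 10.1.1, restrict the death branch of study medication duration to deaths before the final non-SFU visit, and set it to the minimum of (death − first dose + 1) and (last dose − first dose + 28). Subjects who die during SFU then follow the ordinary rule, including the final-visit cut-back, as survivors with the same dosing do. With this wording, the subject with one dose and death 112 days later has at most 28 days, and the subject with four doses on schedule who dies 140 days after the last has 112.

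Optionally, add a footnote to the cumulative table giving the number of days behind each row. It could say that fully dosed completers with an early Week 12 dose, or a Week 16 visit 2 to 3 days early, have 109 to 111 days.

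The cost is one sentence of SAP text, one derivation and, if wanted, a footnote. No new data are needed.
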